7.5.2 Concomitant Medications

The treating investigator or qualified designee will record medication, if any, taken by the subject during the trial.

7.6 Disease Details and Treatments

7.6.1 Disease Details

The treating investigator or qualified designee will obtain prior and current details regarding disease status.

7.6.2 Prior Treatment Details

The treating investigator or qualified designee will review all prior cancer treatments including systemic treatments, radiation and surgeries.

7.6.3 Subsequent Anti-Cancer Therapy Status

The treating investigator or qualified designee will review all new anti-neoplastic therapy initiated after the last dose of trial treatment. If a subject initiates a new anti-cancer therapy within 30 days after the last dose of trial treatment, the 30-day Safety Follow-up visit should occur before the first dose of the new therapy. Once new anti-cancer therapy has been initiated the subject will move into survival follow-up.

7.7 Adverse Event (AE) Monitoring

The treating investigator or qualified designee will assess each subject to evaluate for potential new or worsening AEs as specified in the Trial Flow Chart and more frequently if clinically indicated. Adverse experiences will be graded and recorded throughout the study and during the follow-up period according to CTCAE (v5.0). Toxicities will be characterized in terms regarding seriousness, causality, toxicity grading, and action taken with regard to trial treatment.

7.8 Full Physical Exam

The treating investigator or qualified designee will perform a complete physical exam during the screening period and as indicated in the Trial Flow Chart. Clinically significant abnormal findings should be recorded as medical history.

7.9 Vital Signs

The treating investigator or qualified designee will take vital signs at screening, prior to the administration of each dose of trial treatment and at treatment discontinuation as specified in the Trial Flow Chart. Vital signs should include temperature, pulse, respiratory rate, weight and blood pressure. Height will be measured at screening only.

7.10 Eastern Cooperative Oncology Group (ECOG) Performance Scale

The treating investigator or qualified designee will assess ECOG status at screening, prior to the administration of each dose of trial treatment and discontinuation of trial treatment as specified in the Trial Flow Chart.

7.11 Tumor Imaging and Assessment of Disease

CT or MRI scans will be obtained at baseline. After completion of neoadjuvant nivolumab + ipilimumab treatment a CT or MRI imaging will again be repeated after completion of surgery (prior to starting adjuvant immunotherapy), and repeated every 6 weeks while on adjuvant therapy and every 3 months for 1 year after completing treatment.

7.12 Tumor Tissue Collection and Correlative Studies Blood Sampling

Tumor tissue will be obtained at laparoscopy and at surgical resection. Correlative studies blood sampling for SRMP, osteopontin, CA-125, and circulating tumor cells will be obtained per Trial Flow Chart schedule.

7.13 Laboratory Procedures/Assessments

Details regarding specific laboratory procedures/assessments to be performed in this trial are provided below Laboratory Safety Evaluations (Hematology, Chemistry and Urinalysis) Laboratory tests for hematology, chemistry, urinalysis, and others are specified in Table 4.

Table 4. Laboratory Tests

Hematology	Chemistry	Urinalysis	Other
Hematocrit	Albumin	Blood	Serum β -human chorionic gonadotropin (β -hCG) †
Hemoglobin	Alkaline phosphatase	Glucose	PT (INR)
Platelet count	Alanine aminotransferase (ALT)	Protein	PTT
WBC (total and differential)	Aspartate aminotransferase (AST)	Specific gravity	Total triiodothyronine (T3)
Red Blood Cell Count	Carbon Dioxide (CO_2 or bicarbonate)	Microscopic exam (If abnormal results are noted)	Free thyroxine (T4)
Absolute Neutrophil Count	Calcium	Urine pregnancy test †	Thyroid stimulating hormone (TSH)
Absolute Lymphocyte Count	Chloride		Blood for correlative studies
	Glucose		
	Potassium		
	Sodium		
	Total Bilirubin		
	Total protein		

Hematology	Chemistry	Urinalysis	Other
	Blood Urea Nitrogen		

† Perform on women of childbearing potential only. If urine pregnancy results cannot be confirmed as negative, a serum pregnancy test will be required.

Laboratory tests for screening should be performed within 14 days prior to the first dose of treatment. After Cycle 1, pre-dose laboratory procedures can be conducted up to 72 hours prior to dosing. Results must be reviewed by the treating investigator or qualified designee and found to be acceptable prior to each dose of trial treatment.

7.14 Safety Follow-Up Visit

The mandatory Safety Follow-Up Visit should be conducted approximately 30 days after the last dose of trial treatment or before the initiation of a new anti-cancer treatment, whichever comes first. All AEs that occur prior to the Safety Follow-Up Visit should be recorded. Subjects with an AE of Grade > 1 will be followed until the resolution of the AE to Grade 0-1 or until the beginning of a new anti-neoplastic therapy, whichever occurs first. SAEs that occur within 90 days of the end of treatment or before initiation of a new anti-cancer treatment should also be followed and recorded.

7.15 Follow-up Visits

Subjects who discontinue trial treatment for a reason other than disease progression will move into the Follow-Up Phase and should be assessed every 3 months by radiologic imaging to monitor disease status. Every effort should be made to collect information regarding disease status until the start of new anti-neoplastic therapy, disease progression, death, or end of the study. Information regarding post-study anti-neoplastic treatment will be collected if new treatment is initiated.

7.16 Survival Follow-up

Once a subject experiences confirmed disease progression or starts a new anti-cancer therapy, the subject moves into the survival follow-up phase and should be contacted by telephone every 12 weeks to assess for survival status until death, withdrawal of consent, or the end of the study, whichever occurs first.

7.17 Assessing and Recording Adverse Events

7.17.1 Adverse Event Characteristics

- **CTCAE term (AE description) and grade:** The descriptions and grading scales found in the revised NCI Common Terminology Criteria for Adverse Events (CTCAE) version 5.0 will be utilized for AE reporting. All appropriate treatment areas should have access to a copy of the CTCAE version 5.0. A copy of the CTCAE version 5.0 can be downloaded from the CTEP web site http://ctep.cancer.gov/protocolDevelopment/electronic_applications/ctc.htm
- **Attribution** of the AE:

- Definite (5) – The AE is *clearly related* to the study treatment.
- Probable (4) – The AE is *likely related* to the study treatment.
- Possible (3) – The AE *may be related* to the study treatment.
- Unlikely (2) – The AE is *doubtfully related* to the study treatment.
- Unrelated (1) – The AE is *clearly NOT related* to the study treatment.

7.17.2 Adverse Event Definitions

7.17.2.1 Adverse Event

An adverse event is defined as any untoward medical occurrence in a patient or clinical investigation subject administered a pharmaceutical product and which does not necessarily have to have a causal relationship with this treatment. An adverse event can therefore be any unfavorable and unintended sign (including an abnormal laboratory finding, for example), symptom, or disease temporally associated with the use of a medicinal product or protocol-specified procedure, whether or not considered related to the medicinal product or protocol-specified procedure. Any worsening (i.e., any clinically significant adverse change in frequency and/or intensity) of a preexisting condition that is temporally associated with the use of the study treatment, is also an adverse event.

Changes resulting from normal growth and development that do not vary significantly in frequency or severity from expected levels are not to be considered adverse events. Examples of this may include, but are not limited to, teething, typical crying in infants and children and onset of menses or menopause occurring at a physiologically appropriate time.

Adverse events may occur during the course of the use of the study treatment in clinical trials or within the follow-up period specified by the protocol, or prescribed in clinical practice, from overdose (whether accidental or intentional), from abuse and from withdrawal.

Adverse events may also occur in screened subjects during any pre-allocation baseline period as a result of a protocol-specified intervention, including washout or discontinuation of usual therapy, diet, placebo treatment or a procedure.

Progression of the cancer under study is not considered an adverse event unless it is considered to be drug related by the treating investigator.

All adverse events will be recorded from the time the consent form is signed through 30 days following cessation of treatment and at each examination on the Adverse Event case report forms/worksheets.

7.17.2.2 Serious Adverse Event

An adverse event is considered serious if it results in **ANY** of the following outcomes:

- 1) Death
- 2) Life-threatening (e.g. places subject at immediate risk of death, this does not include events that might have caused death if they occurred a greater severity)
- 3) Inpatient hospitalization or prolongation of existing hospitalization for ≥ 24 hours

- 4) A persistent or significant incapacity or substantial disruption of the ability to conduct normal life functions
- 5) A congenital anomaly/birth defect.

7.17.2.3 Adverse Reactions

An adverse event is considered to be an adverse reaction if there is evidence to suggest a causal relationship to the study agent. This may include a single occurrence of an event strongly associated with drug exposure (e.g. Stevens-Johnson Syndrome), one or more occurrence of an event otherwise uncommon in the study population, or an aggregate analysis of specific events occurring at greater than expected frequency.

7.17.3 Evaluating Adverse Events

An investigator who is a qualified physician will evaluate all adverse events according to the NCI Common Terminology for Adverse Events (CTCAE), version 5.0. Any adverse event which changes CTCAE grade over the course of a given episode will have each change of grade recorded on the adverse event case report forms/worksheets.

All adverse events regardless of CTCAE grade must also be evaluated for seriousness.

7.17.4 Responsibility for Reporting Adverse Events

All Adverse Events will be reported to regulatory authorities, IRB/IECs and investigators in accordance with all applicable global laws and regulations.

8.0 STATISTICAL ANALYSIS PLAN

8.1 Primary Endpoint

The primary endpoint in this study is Major Pathologic Response (MPR), defined as presence of $\leq 10\%$ residual viable tumor in the resected surgical specimen. The proportion of patients who achieve an MPR will be reported (MPR rate), along with an exact 95% confidence interval.

Sample size considerations: A total of 37 patients will be enrolled, with the goal to enroll 18-19 patients per year in 2 consecutive years. This sample size will provide 80% power to detect a significant increase in MPR rate of at least 40% using the one-sided binomial test with the null hypothesis $H_0: p = 0.5$ against the alternative hypothesis $H_a: p > 0.5$ corresponding to an actual MPR rate of ~ 0.7 or higher.

8.2 Secondary Endpoints

Safety and feasibility will be assessed throughout the trial, especially in discussion with the surgeon performing the cytoreductive surgery. Adverse events will be summarized by type, grade, and relationship to the study drug. The trial will be discontinued if the 30-day mortality occurs in two patients and the cause of death is determined to be related to the investigational agent by the treating medical oncologist and surgeon. Refer to section 6.8 for additional clinical criteria for early trial termination.

Analyses to address the secondary objectives will be primarily descriptive in nature. Progression-free survival (PFS) and overall survival (OS) will be estimated using the Kaplan-Meier method with qualitative assessment of the emergence of a tail at the end of the curve as evidence of long-term survival, which is not seen in this disease despite aggressive multimodality therapy. Median event times will be determined as the time at which the Kaplan-Meier curve falls below 50%.

The objective response rate to neoadjuvant nivolumab + ipilimumab based on cross-sectional imaging pre- and post-treatment will be determined along with an exact 90% confidence interval.

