2.2 Secondary Objectives

1. To determine the safety profile of neoadjuvant nivolumab + ipilimumab, as defined by rate of grade III/IV adverse events according to CTCAE v5.0, occurring up to 30 days post-operatively.
2. To determine feasibility of neoadjuvant nivolumab + ipilimumab, as measured by the number of participants who complete neoadjuvant treatment with nivolumab + ipilimumab and proceed to surgery without extended treatment-related delay (> 6-week delay) or progression precluding surgery.
3. To determine the Overall Survival (OS) effect from neoadjuvant nivolumab + ipilimumab, defined as time from enrollment on study to death from any cause.
4. To determine the Progression-free Survival (PFS) effect from neoadjuvant nivolumab + ipilimumab, defined as time from enrollment on study to disease progression or death.

5. To determine the safety profile of adjuvant nivolumab + ipilimumab after cytoreductive surgery and HIPEC.
6. To determine the radiologic response to neoadjuvant nivolumab + ipilimumab utilizing RECIST 1.1 pre- and post-treatment.
7. To determine the effect of neoadjuvant nivolumab + ipilimumab on peritoneal carcinomatosis index (PCI).

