3.2 Rationale

3.2.1 Rationale for the Trial and Selected Subject Populations

Around 500-800 new cases of peritoneal mesothelioma occur every year in the United States (Miura, 2014). In contrast to pleural mesothelioma, an antecedent exposure to asbestos cannot always be found in patients with this disease. However, we previously demonstrated that germline mutations (with *BAP1* mutations being most common) are found in as many as 25% of peritoneal mesothelioma patients, compared to only 7% of those with pleural disease (Panou, 2018), implying that inherited susceptibility may play a larger role in peritoneal mesothelioma. Patients generally present with ascites or malignant bowel obstructions, which are significantly life limiting due to the resulting malnutrition and inanition. Cross sectional imaging such as CT scans or MRIs are

utilized in the diagnosis of peritoneal mesothelioma but they generally underestimate the burden of disease. There are 3 major histologic subtypes of mesothelioma: epithelial, sarcomatoid, and mixed or biphasic (Husain, 2009). Pathologic subtype is one of the most important prognostic indicators in this disease, so an accurate determination of pathology is essential (Rusch, 2012).

The prognosis of patients with peritoneal mesothelioma is rather dismal in the absence of treatment, with a median survival of 12 months (Alexander, 2013). The standard of care for patients with peritoneal mesothelioma is the performance of cytoreductive surgery (CRS) and hyperthermic intra-peritoneal chemotherapy (HIPEC). The surgery consists of extirpation of peritoneal tumor with parietal and visceral peritonectomy procedures and visceral resections as necessary. During the surgery, the burden of disease is assessed by the peritoneal cancer index (PCI score). This score is measured by dividing the abdomen into 13 zones (including 4 zones for the bowel) and ranges from 0-39 (39 being the most disease). At the end of the operation the residual tumor is assessed by the completeness of cytoreduction which is an important prognostic factor for the survival of these patients. Heated chemotherapy is then applied to the peritoneal surfaces for 90 minutes and circulated at 600 ml-1500ml/min at 42 °C (Turaga K 2016).

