Patients undergoing CRS+HIPEC have an overall median survival of 53 months, with a more favorable prognosis for patients that undergo a complete cytoreduction (CC-0/1)(Yan TD 2009). The agent of choice for the intra-operative chemotherapy is either platinum based (cisplatin/carboplatin) or mitomycin C (Helm, 2015). Grade III-IV complication rates after this surgery can be as high as 31-40% (Kepenekian 2016). Major complications include death, anastomotic leak, deep or superficial site infection, anemia, re-operations, organ failure including renal failure, cardiac failure or respiratory failure, neutropenia, thromboembolic events, dehydration and failure to thrive.

Due to the relatively low incidence of peritoneal mesothelioma, there are no large randomized controlled trials for either surgery or chemotherapy to guide management, leaving no clear consensus on optimal treatment approach. Therefore, much of the management is extrapolated from the studies in pleural mesothelioma. Standard chemotherapy for pleural mesothelioma consists of pemetrexed plus cisplatin. This regimen was FDA-approved for MM based on a single-blind, placebo-controlled, phase III trial, which randomized 456 patients to cisplatin with or without pemetrexed. Patients who received the combination achieved a longer median overall survival (12.1 vs. 9.3 months, $p = 0.020$), a superior time to progression (5.7 vs. 3.9 months, $p = 0.001$), and a higher objective response rate (41% vs. 17%, $p < 0.001$) than patients who received cisplatin alone (Vogelzang, 2003).

However, the benefits of cytotoxic chemotherapy for peritoneal mesothelioma are less clear and alternative therapies such as immunotherapy warrant investigation. PD-1/PD-L1 and CTLA4 are immune checkpoints that mediate immune evasion in a wide spectrum of tumors. While the normal function of PD-1 and CTLA4 is to counteract excessive immune responses directed against normal tissues, various types of cancer have manipulated this function by up-regulating the natural ligands of these checkpoints to evade immune recognition. The critical role of this pathway became evident with the promising results of clinical trials of PD-1/PD-L1 and CTLA4 inhibitors, such as pembrolizumab (Hamid, 2013), nivolumab (Wolchok, 2013), and MPDL3280A (Powderly, 2013). While immune checkpoint blockers have not been evaluated in mesothelioma in the neoadjuvant setting, they are being used safely in the preoperative setting in a variety of tumor types.

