Based on these and other studies, MM is an ideal target disease for anti-PD-1 therapy, and further investigation of the biology of this agent in this disease is warranted. This hypothesis is further supported by the recently reported data from the CheckMate 743 study. This was a randomized, open-label trial in patients with unresectable malignant pleural mesothelioma, with a primary endpoint of overall survival. Patients were randomized to receive either combination immunotherapy with nivolumab + ipilimumab for up to 2 years or standard chemotherapy with pemetrexed + either cisplatin or carboplatin for 6 cycles. The trial demonstrated a statistically significant improvement in OS for patients randomized to immunotherapy compared to chemotherapy. While it was efficacious in all histologies, there was a greater benefit noted in the sarcomatoid subgroup. The results of this trial have established a new standard of care in the treatment of malignant pleural mesothelioma, with immunotherapy now considered first line therapy. (Baas 2020).

Therefore, we expect to see a similar response to immunotherapy in the peritoneal disease setting, and with this study we aim to evaluate that response. Of note, while resection is typically offered only to patients with non-sarcomatoid histology, in this trial we plan to include sarcomatoid histologies as well. Due to the robust response in the CheckMate 743 trial, which demonstrated that immunotherapy allowed for an equivalent survival in the sarcomatoid cohort to the epithelioid cohort, we anticipate that the sarcomatoid peritoneal patients will have a similar response, making their disease more amenable to cytoreduction.

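### Section 8.2 reads an undefined, eye-judged Kaplan-Meier tail as evidence of long-term survival; for OS, 37 patients followed about 18 to 42 months cannot support that inference (minor)

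*Combined protocol and SAP*

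**What the plan says.** Section 8.2 estimates OS and PFS by Kaplan-Meier "with qualitative assessment of the emergence of a tail at the end of the curve as evidence of long-term survival", and says of this "which is not seen in this disease despite aggressive multimodality therapy". No source or figure accompanies that premise. The section reports medians: "Median event times will be determined as the time at which the Kaplan-Meier curve falls below 50" per cent. It specifies no survival rate at a fixed time, no confidence interval for either curve, no number at risk and no definition of a tail. By contrast, exact intervals are specified for MPR (Section 8.1) and for objective response (Section 8.2). The section also states: "Analyses to address the secondary objectives will be primarily descriptive in nature".

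OS is "defined as time from enrollment on study to death from any cause" (Section 2.2). The Trial Summary estimates 24 months of enrollment and a 42-month trial, and Section 4.1 repeats the 42 months. Section 7.16 ends survival contact with the study at the latest. As background, Section 3.2.1 states: "Patients undergoing CRS+HIPEC have an overall median survival of 53 months".

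**The concern.** Describing the end of a curve is harmless. Section 8.2 goes further and says in advance what a tail will mean. The last part of a Kaplan-Meier curve rests on the few patients enrolled first, and it is flat whenever none of them happens to die late. If the benchmark median is longer than the whole trial, a high, flat end is expected even when hazard never falls.

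At stake is the survival statement in the final report. Following the plan as written, a flat end that arises with no plateau could be reported as evidence of long-term survival, with nothing beside it to show how few patients it rests on.

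**Working it through.** The plan gives no figure for the tail, so there is none to reproduce. The check asks how often a tail appears without a plateau, and how much more often with one.

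**Inputs from the documents**
- N = 37 (Section 8.1).
- Accrual 24 months, trial 42 months (Trial Summary, Section 4.1). Follow-up therefore runs from 42 − 24 = 18 months to 42 months. This is derived, not stated.
- Median OS 53 months with CRS+HIPEC (Section 3.2.1).

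**Assumptions**
- Uniform accrual, no dropout, exponential OS with λ = ln 2 / 53 = 0.01308 per month.
- Tail = longest follow-up time minus time of last death.
- A plateau means that 30% never die.

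**Numbers at risk** = 37 × share enrolled early enough × S(t), where S(t) = exp(−λt)
- Month 24: 37 × 18/24 × 0.731 = 20.3
- Month 30: 37 × 12/24 × 0.675 = 12.5
- Month 36: 37 × 6/24 × 0.624 = 5.8

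Even zero deaths among 6 patients is compatible with an event probability up to 1 − 0.025^(1/6) = 46% (two-sided 95% limit).

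**Chance of a flat end (simulation, 100,000 trials per scenario)**

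| OS scenario | ≥6 months | ≥12 months | ≥18 months |
|---|---|---|---|
| No plateau, median 53 | 73% | 33% | 8% |
| 30% never die, overall median held at 53 | 76% | 36% | 9% |
| 30% never die, median 53 in the others | 81% | 46% | 18% |
| Ratio, plateau to no plateau | 1.0–1.1 | 1.1–1.4 | 1.2–2.2 |

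In the second row, 0.3 + 0.7·exp(−53L) = 0.5 gives L = ln 3.5 / 53, a median of 29.3 months in those who do die. The first plateau row isolates curve shape at an unchanged median. The second also lengthens survival overall, so it favours the tail more.

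**Sensitivity**
- Cut at month 50: without a plateau, 74%, 36% and 10%. At risk at month 36: 37 × 14/24 × 0.624 = 13.5.
- Shorter OS medians without a plateau: 67%, 25% and 4% (36 months); 61%, 19% and 2% (24 months); 48%, 15% and 2% (12 months, the figure Section 3.2.1 gives for untreated disease).

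**PFS.** The documents give no median. Under assumed medians of 12 to 24 months without a plateau, a flat end of at least 6, 12 and 18 months appears in 48–61%, 16–19% and about 2% of trials. With 20–50% never progressing, the ratios are 1.2–1.8, 1.5–3.6 and 2.6–12.

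**The case against.** The strongest reply is that the analysis is labelled descriptive, no decision depends on it, and numbers at risk and intervals can be added at reporting. That stands as to weight. It does not remove the fault, because a rule for reading a tail as evidence is an inference, whatever label the section carries.

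Several stronger readings are tempting, and the documents do not support them.

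- *The 53-month median disproves the premise.* It does not. A median says nothing about whether a plateau occurs later. The premise is uncited, but not shown to be false.
- *Every tail is nearly worthless.* This is shown for OS only. For an endpoint with a shorter median, a tail of 18 months or more can be informative: with an assumed 12-month median and half the patients never progressing, the ratio reaches about 12. Section 8.2 requires no such length, however.
- *The plan uses the tail to claim drug benefit.* Section 8.2 speaks of long-term survival, not of an effect over a comparator. The ratios above therefore compare plateau with no plateau.
- *Only about 6 patients will be at risk at month 36.* That depends on the 42-month figure, which the Trial Summary calls estimated. A cut at month 50 roughly doubles the number, though tail frequencies without a plateau barely change.

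The figures also rest on an exponential model, since only a median is cited. The trial population may differ from the benchmark: "in this trial we plan to include sarcomatoid histologies as well", OS starts at enrollment, and some patients may not reach surgery.

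**Conclusion.** The concern holds for OS as a minor point. At the protocol's own median, a flat end of 6 months or more is the usual result with or without a plateau. One of 12 or 18 months is rarer, but at most about 1.4 and 2.2 times as frequent when 30% never die. Nothing in Section 8.2 separates a tail that means something from one that does not. For PFS, the claim is limited to short tails, under assumed medians.

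This rests on exponential survival, uniform accrual, no dropout and a cut near month 42. The primary MPR analysis and the sample size are unaffected.

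**What to change.** In Section 8.2, delete the statement that a tail is evidence of long-term survival, together with the uncited premise. Add Kaplan-Meier OS and PFS at 12, 18 and 24 months with 95% confidence intervals, numbers at risk and median follow-up. Beyond month 24, show the curve only with its number at risk and interval, and infer no long-term survival from it. Keep any comparison with the 53-month median descriptive, and state the population differences.

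If accrual finishes on time, every patient can reach 12 and 18 months by month 42, and 18/24 of them (about 28 of 37) can reach 24 months. The later landmark loses little OS precision. By Greenwood's formula, with the share under observation G(t) = 1 up to month 18 and (42 − t)/24 afterwards, Var(S)/S² = (1/37)∫λe^{λt}/G(t)dt:
- Month 18: SE = 0.790 × √(0.2654/37) = 0.067, or about ±13 points.
- Month 24: SE = 0.731 × √(0.3845/37) = 0.074, or about ±15 points.

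These landmarks do not establish long-term survival either; they report what the design can estimate. The change needs no extra patients, visits or time. Its one cost is a less favourable survival statement.

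A separate minor item: the Trial Summary gives 18 months of participation and a 42-month trial, while Sections 1.1, 5.4 and 7.11 imply a schedule of roughly 25 to 28 months per patient. These and Section 4.1 should be reconciled.
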